Using a chi-square test and setting alpha at 0.05, the probability of detecting a statistically significant difference in the proportion of children with symptoms of any FGID with improvement in the primary outcome at 3 months from baseline between the intervention and the control group is 90%, with an effective sample size of 163 per group. Hence, the total effective sample size (n\*) is 326.

The unit of randomization is the clinic, but the unit of analysis is the individual patient. Since patients are nested within practice, responses from the patients within practice are likely to be

correlated. This intra-cluster correlation must be taken into account in the calculation of sample size and in the analyses. We computed the number of patients per clinic,  $m$ , required for the study, using the following equation:

$$m = \frac{1 - \rho}{\frac{k}{n^*} - \rho}$$

where  $\rho$  = intra-practice correlation  
 $k$  = number of clinics  
 $mk$  = total sample size  
 $n^*$  = total effective sample size =  $mk/DE$   
and  $DE$  = design effect =  $1 + \rho(m-1)$

Using 6 clinics and assuming intra-class correlation of 0.014, we need to recruit 224 families with a child between 0 and 18 per clinic. We anticipate that drop-out is not a major problem and unlikely to be more than 10% for the primary outcome. We will account for this factor by oversampling patients by 10%. According to the data presented in Table 3 and with an assumption that for each category of FGID diagnosis 50% of the patients will be in the control clinics and other 50% will be in intervention clinics, there will be about 5,500 patients/year/group with a FGID diagnosis. If we assume that only 66% of the parents will respond to the phone call at 3-month post baseline, we will have 3,630 patients/year/group. Therefore, the number of patients from which we are able to recruit is not a factor at all. We can have more than 90% power even to detect a 5% absolute difference with all available patients in one year.

**Data Analysis.** Baseline clinical and demographic data will be compared between the intervention and the control groups. Categorical variables will be examined using chi-square tests and continuous measures with Student's t-tests. The statistical analysis of the data will be performed using the SAS.

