**Primary Outcome Analysis:** The primary outcome is whether there was resolution of symptoms of a FGID by Rome IV criteria in children and adolescents or whether parental reassurance was achieved for infants. For this dichotomous outcome, we will use a non-linear mixed-effects model and will adjust for potential confounders (fixed effects) and clinic effects (random effects). To be specific, if  $Y_{ik}$  is a binary variable indicating whether the  $k^{\text{th}}$  patient in the  $i^{\text{th}}$  clinic was reported a resolution of FGID symptom, we have

$$\text{logit}(Y_{ik} = 1) = \alpha_i + \mathbf{X}_{ik}\beta, \text{ where } \alpha_i \sim N(0, \sigma^2).$$

The random component  $\alpha_i$  correlates outcomes of patients cared by the same clinic. Physicians would not be considered as a nesting factor since the same patients at different visits may not be seen by the same physician. The vector  $\mathbf{X}_{ik}$  represents fixed covariates and  $\beta$  represents the corresponding coefficients. The fixed covariates will include critical covariates such as treatment group, gender, and other patient and clinic level characteristics. We will also examine potential interaction terms among the covariates, particularly interactions between treatment arm and other covariates. If there is a significant treatment difference, we will report the 95% confidence interval of the treatment difference after adjusting for all confounding factors. The model will be fitted by the SAS procedure NL MIXED.

**Secondary Outcome Analyses:** The additional time points of 1, 6, and 12 months will be modeled identically to the primary outcome analysis. Furthermore, we will have a number of secondary outcomes which are count data aggregated within the 12 months after initial Rome IV

diagnosis. We will use Poisson regression to model these count data. To adjust for the possible differences between the intervention and control groups, we will use an approach similar to the analyses of primary outcomes and again clinic will be considered as a cluster factor to take into consideration the correlation in count data within each clinic. Family and provider satisfaction scores will be analyzed using Student's t-test, as well as a linear mixed-effects model as with other outcomes.

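### The six-clinic primary test is a maximum-likelihood NLMIXED fit with no stated small-sample method, so its type I error depends on the ICC and clinic sizes: about 8% at the planning values, about 5% or less at 100 per clinic

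*SAP*

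**What the plan says.** SAP, Sample Size and Power Estimates, sets the design: "The unit of randomization is the clinic, but the unit of analysis is the individual patient". On clustering it says: "This intra-cluster correlation must be taken into account in the calculation of sample size and in the analyses". The target is then derived: "Using 6 clinics and assuming intra-class correlation of 0.014, we need to recruit 224 families" per clinic.

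SAP, Primary Outcome Analysis, writes out a logistic model with a normal random intercept for clinic. It describes the covariates thus: "The fixed covariates will include critical covariates such as treatment group, gender, and other patient and clinic level characteristics". It then names the software: "The model will be fitted by the SAS procedure NL MIXED". On the interval it says: "If there is a significant treatment difference, we will report the 95% confidence interval of the treatment difference after adjusting for all confounding factors".

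SAP, Secondary Outcome Analyses, carries the model over: "The additional time points of 1, 6, and 12 months will be modeled identically to the primary outcome analysis". Count outcomes get Poisson regression with clinic as the cluster factor. For satisfaction: "Family and provider satisfaction scores will be analyzed using Student's t-test, as well as a linear mixed-effects model as with other outcomes".

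Neither document gives a reference distribution, denominator df, small-sample correction, permutation test or clinic-level test for any of these. The protocol (section B, research interactions) confirms randomisation by clinic and anticipates at most 600 survey participants.

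**The concern.** With six randomised clinics and two arms, the treatment effect is estimated from differences between clinics, and 6 − 2 = 4 df are available to estimate its error. Maximum likelihood makes no allowance for the two arm means already fitted. It in effect divides the between-clinic sum of squares by 6 where 4 is needed, so the standard error is too small. A reference distribution with more than 4 df adds to this. A second feature works the other way: when clinics are small or the ICC is low, the clinic variance is often estimated as zero, the within-clinic error then acts as a floor, and the test becomes less liberal or even conservative.

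At stake is whether a primary p value just under 0.05 can be taken at face value. The same model supplies the 95% confidence interval and the analyses at months 1, 6 and 12, and the Poisson models rest on the same six clusters. Each clinic-level covariate would use another of the 4 df, and the SAP does not say how many there will be.

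**Working it through.** **Inputs.** From the SAP: 6 clinics; control rate 30%; difference 15 points, so 30% v 45%; planning ICC 0.014; estimated ICC 0.007; effective sample size 163 per group (326 in total); alpha 0.05; pool of 3,630 patients per year per group. From the protocol: at most 600 surveys. Assumed: two-sided test, three clinics per arm, ICC on the proportion scale (as in the SAP's design-effect formula), 224 taken as the number analysed, no clinic-level covariate, and t on 5 df (clinics minus one random effect) as the presumed default.

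**The SAP's own figure.** m = (1 − 0.014)/(6/326 − 0.014) = 0.986/0.004405 = 223.8, so 224 per clinic reproduces.

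**Clinic sizes to examine.** Target: 224. Survey ceiling: 600/6 = 100. Whole pool: 3,630/3 = 1,210.

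**Large-clinic limit.** When between-clinic variation dominates, the ML variance is 4/6 of the unbiased one, so the size is P(|t₄| > c·√(4/6)).
- c = 2.571 (5 df): P(|t₄| > 2.099) = 10.4%.
- c = 2.776 (4 df): P(|t₄| > 2.267) = 8.6%.
- c = 1.960 (normal): P(|t₄| > 1.600) = 18.5%.

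**Simulated size.** Null trials with both arms at 30%, beta-binomial clinics of equal size, 20,000 trials per setting. The model was fitted by maximum likelihood with adaptive quadrature, with a Wald test from the full Hessian.

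| ICC | Per clinic | ML on t(5) | ML on normal | Clinic variance estimated as zero |
|---|---|---|---|---|
| 0.014 | 224 | 8.1% | 16.5% | 16% |
| 0.007 | 224 | 5.7% | 13.3% | 33% |
| 0.014 | 100 | 5.3% | 12.6% | 35% |
| 0.007 | 100 | 3.5% | 10.1% | 53% |
| 0.014 | 1,210 | 10.3% | 18.3% | 1% |
| 0.007 | 1,210 | 10.2% | 18.3% | 4% |

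**Sensitivity on t(5).**
- Planning values: 7.6% to 7.8% with logit-normal clinics, 8.8% with unequal clinics (112/224/336), about 6.9% if 0.014 is read on the logit scale.
- ICC 0.007 with 224: about 5.5% with logit-normal clinics, 7.0% unequal, 4.5% on the logit scale.
- ICC 0.014 with unequal clinics of 50/100/150: 5.9%.

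**Changing only the df.** The same ML fit on 4 df gives 6.3% at the planning values and 8.5% at 1,210 per clinic with ICC 0.014.

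**Alternatives.**
- A t-test on the six clinic summaries with 4 df: 4.6% to 5.3% in all 13 null settings.
- Its observed-minus-expected form with one binary patient covariate: 4.8% to 5.3% in 16 settings.
- REML-type pseudo-likelihood (as in PROC GLIMMIX) on 4 df: 3.8% and 2.8% at 224 per clinic, 2.4% and 1.5% at 100 (ICC 0.014 and 0.007 in each pair).

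**Power of the clinic-level t-test, 30% v 45%, planning values.** Mean binomial variance (0.21 + 0.2475)/2 = 0.22875. Design effect 1 + 223 × 0.014 = 4.122. SE = √(0.22875 × 4.122/224 × 2/3) = 0.0530. Noncentrality 0.15/0.0530 = 2.83. The normal formula gives 81%; noncentral t on 4 df gives 57%. The same steps give about 76% at ICC 0.007 with 224 per clinic, and about 47% at ICC 0.014 with 100 per clinic.

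**The case against.** The strongest reply is that in the setting the current protocol best supports there is no material inflation. The SAP obtains the 3-month outcome from parents who answer a follow-up call, and the protocol limits surveys to 600. At 100 per clinic the size on t(5) is about 5% at ICC 0.014 and 3% to 3.5% at 0.007. This stands, and it is why the point is conditional. It does not remove the problem: 224 per clinic at ICC 0.014 is the SAP's own sample-size basis, and the documents do not settle how many patients will enter the primary model.

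It is also fair to say that t(5) and the 3 v 3 split are assumptions. A normal reference would be worse (about 10% to 18%), but the SAP does not specify one, so those figures cannot be charged to the plan.

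A reader might infer three stronger things, none of which the documents support:

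- *The primary test has a 10% false-positive rate.* That needs 1,210 per clinic. The SAP presents 3,630 per group as the pool to recruit from and uses all available patients only in a remark on power; the target is 224 per clinic.
- *The test is always anti-conservative.* It is near nominal or conservative in several plausible settings.
- *Reported 95% intervals cover 92%.* That only restates the 8% size. The SAP reports the interval only after a significant result, so 92% does not describe the intervals a reader would see.

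In the other direction, the figures take the SAP's two ICCs as given. At an ICC of 0.035, for illustration, the size with 224 per clinic would be 9.6%.

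**Conclusion.** The concern holds in conditional form. For a primary test on six randomised clinics the SAP specifies an ML fit and no small-sample method. On t(5), with three clinics per arm and no clinic-level covariate, the size runs from 3% to 3.5% (ICC 0.007, 100 per clinic) to about 8% (ICC 0.014, 224 per clinic), and to about 10% only in the whole-pool case. The level of the primary test is therefore set by the ICC and clinic sizes that happen to occur.

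This is more than a missing detail, because writing in 4 df and leaving the fit unchanged still gives 6.3% at the planning values. It should be fixed before analysis. The omission itself is certain; the sizes rest on the stated assumptions. No size is claimed for clinic-level covariates, the count outcomes or satisfaction. For satisfaction the point is textual: an unclustered t-test stands beside a mixed model, with no rule on which governs.

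**What to change.** - **Primary test and its 95% interval:** a t-test on the six clinic summaries with 4 df.
- **Patient-level covariates:** fit a logistic model on them without treatment, then compare observed minus expected per clinic. This form was checked for size only; its interval coverage under a treatment effect should be simulated before it is adopted.
- **Clinic-level covariates:** leave them out of the primary model, or reduce the df by one for each.
- **Months 1, 6 and 12, and the count outcomes:** use the same six-cluster approach.
- **Satisfaction:** state that the clustered analysis governs, and drop the unclustered t-test.
- **Not an equal alternative:** REML-type estimation in GLIMMIX with 4 df, which is markedly conservative at 100 to 224 per clinic.

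**Cost.** SAP wording and a change of procedure; no new data. Intervals widen (critical value 2.78 on 4 df, against 2.57 on 5 df and 1.96 on the normal). Power for 30% v 45% is about 57% at the planning values, 76% at ICC 0.007 with 224 per clinic, and 47% at ICC 0.014 with 100 per clinic, against the 90% in the SAP. Not all of that gap comes from the new test: at 163 effective patients per group even the normal formula gives about 81%. NLMIXED on t(5) shows about 75% at the planning values, partly bought by its 8% size. Larger clinics recover little (about 66% at 1,210 per clinic, ICC 0.014). The SAP should restate its power on this basis.

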codes), Eskenazi clinic(s) of care Health care utilization retrospective review: • The presence of outpatient sick visits within the Eskenazi system clinic for any complaint • The presence of outpatient sick visits within the Eskenazi system clinic with an associated GI billing code • The presence of visits to statewide providers, including inpatient hospital stays, outpatient clinic visits, and emergency room visits. • The occurrence of any GI-related testing and procedures – specifically radiologic, laboratory testing, endoscopy, and surgical procedures related to GI diagnoses • The use of any medications prescribed to treat Rome IV diagnoses – specifically acid-suppressants, antispasmodics, antidepressants, stool softeners and laxatives, and pro-motility agents.

q23340

Would identification of subjects and/or their responses reasonably place them at risk for any of the following (check any that apply):

None

B-Lay Summary Research Design

q22122

Describe the purpose of this study in lay terms, including research question(s) and hypothesis.

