or presents to any primary care clinics in the Eskenazi health system which support general pediatric care, the patient (and/or parent) will be asked to complete FGID screening questions prior their provider visit as part of standard care. Rules have been established within EPIC to determine how often patients receive the FGID questionnaire to avoid redundancy, inappropriate use, and/or burden to the patient. Screening results will be available to physicians immediately, and physicians in the intervention clinics will have access to specific guidance for the diagnosis and treatment/management of the FGID, as well as information to share with families. Physicians may chose to document their FGID assessments and plans in the patient's EMR via EPIC. We hypothesize that automation of screening, diagnosis, and management of FGIDs will result in improved resolution of FGIDs (primary outcome), as well as decreased utilization of medical services (secondary outcomes). We propose to test this hypothesis using the following specific aims: Aim 1: Develop computer-based decision support system, to screen children 0 to 18 years of age for functional gastrointestinal disorders (FGIDs) using the Rome IV criteria, and provide guidance regarding diagnosis and management of probable FGIDs. (Please note that Aim 1 does not involve the use of human subjects/PHI.) Aim 2: Demonstrate the feasibility and effectiveness of the FGID Module to improve clinical care measures (e.g., resolution of Rome IV criteria) and reduce utilization of healthcare services (e.g. repeat outpatient visits, ED visits).

q22123

List and describe all research interactions and/or interventions, including the frequency and duration of procedures, and length of participation for individual subjects.

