The PI affirms that translated versions are complete and accurate translations which do not contain information not presented within the context of the English version(s).

Yes

q24919

Is this research funded by, or has a funding application been submitted to, a federal agency? This includes federal pass-through funding.

Yes

q25019

Provide the name of the federal funding agency.

q23234

List inclusion criteria - eligibility criteria for subjects.

FGID module: Any child between the ages of 0 through 18 who is a pediatric primary care clinic in the Eskenazi health system and the PCP/physician who sees them A002

Tool usability questionnaire: A subset of patients who completed the FGID module between age 0 and 17 Survey (online and phone): A subset of patients with a positive screen for a FGID and their parents between age 0-17 Baseline retrospective review:

Any patient ages 0-18 who presented to a a pediatric primary care clinic in the

Eskenazi health system prior to the implementation of the FGID module Health care

utilization retrospective review: Any patient ages 0-18 who presents to a pediatric

primary care clinic in the Eskenazi health system after the implementation of the

FGID module

q23235

List exclusion criteria (any criteria which would exclude otherwise acceptable subjects).

FGID module, retrospective reviews: none A002 Tool usability questionnaire: does not meet inclusion for FGID module and did not complete the module Survey (online

and phone): Parent and patient be able to provide consent/assent in English or Spanish. We do not currently have the resources to include participants who speak a language other than English and Spanish.

q23346

Will subjects be paid for their participation in the study? Payment includes reimbursement of expenses (other than compensation for injury).

Yes

q23347b

Describe the payment arrangement, including amount and timing of disbursement.

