FGID module, retrospective/prospective reviews: We are requesting a waiver of consent for this part of the research. Patients and parents will be asked (but not required) to respond to yes/no questions about GI symptoms as part of standard care. No part of this research presents more than a minimal risk to subjects. Study team personnel have been trained in human subjects' research practices and HIPAA regulations (i.e. confidentiality, privacy and security practices). Furthermore, all data will be securely transferred and stored on fire-walled, encrypted and password-protected hard drives and databases, and locked file cabinets will be used to store any confidential paper study materials.

q933

Explain how the waiver will not adversely affect the rights and welfare of subjects.

FGID module, retrospective/prospective reviews: The waiver will not adversely affect the rights and welfare of subjects as we are only (securely) accessing and using data generated in a clinical setting under standard care.

q905

Explain how the research could not be practicably carried out if informed consent were required.

FGID module, retrospective/prospective reviews: If informed consent were required, we could not practicably obtain consent from the patients who answer module questions or whose data is used in the retrospective reviews as there are no study staff present in clinics.

q30004b

Explain why the research could not be practicably carried out without identifiers.

FGID module, retrospective/prospective reviews: Without identifiers, we could not conduct the research because we need to link patient encounter data to past and prospective health data to look at patient outcomes.

q914

Explain how subjects will be informed of pertinent results at the conclusion of the study, if appropriate. If subjects will not be informed, enter N/A.

N/A

q23678a

For those subjects who will consent to participate, choose whether the consent process will be documented by a written signature from subjects.

Some subjects will provide a written signature as documentation of consent, and some subjects will not.

q30129a

Will subjects participate in any study activity prior to physically signing a consent document?

No

q939a

Explain which subjects will provide a written signature as documentation of consent, and which subjects will not.

Survey participants who enroll online will be asked for a printed (typed) signature.

q940b

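### Reducing health-care use is a stated aim, but no pre-screen utilisation is specified as data or covariate, and the listed yes/no items do not match the counts that the SAP models

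*SAP*

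**What the plan says.** **Aim.** In the protocol (section B, q22122), Aim 2 is in part to "reduce utilization of healthcare services (e.g. repeat outpatient visits, ED visits".

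**Outcome and model.** Under Secondary Outcome Analyses the SAP states that "we will have a number of secondary outcomes which are count data aggregated within the 12 months after initial Rome IV" diagnosis. It continues: "We will use Poisson regression to model these count data". On adjustment it says: "To adjust for the possible differences between the intervention and control groups, we will use an approach similar to the analyses of primary outcomes", with clinic as a cluster factor. The fixed covariates given for the primary model are "treatment group, gender, and other patient and clinic level characteristics". Prior use is not named.

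**Who and when.** The utilisation review takes in children who present to a "primary care clinic in the Eskenazi health system after the implementation of the" module (section B, q23234). Section D, q23236 identifies them by a positive screen. The one review of the period before implementation (q22123, with its data points in q725 and q23650) collects date of birth, dated diagnosis codes and clinic, to estimate the prevalence of diagnoses. It collects no visits, tests or drugs.

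**Data points.** The first utilisation item in q725 is "The presence of outpatient sick visits within the Eskenazi system clinic for any complaint". Testing is listed as the occurrence of any, and medication as the use of any. The same form of words recurs in section K, q23650, and in item 9010 of the Administrative Details Form.

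**Access to earlier records.** Section H, q30004b justifies identifiers on the ground that "we need to link patient encounter data to past and prospective health data to look at patient outcomes"; q30004d repeats this.

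**The concern.** Clinics differ in how often their patients attend, are tested or go to an emergency department, and some children are persistently heavy users. With six randomised clinics and no stratification, matching or constraint described, the arms may differ noticeably in usual use before the module has any effect. Prior use of the same service is the obvious covariate for such an outcome, and the sources already to be queried, Epic and the Indiana Network for Patient Care (INPC), are a natural place to find it. If it is not collected, the utilisation comparison is noisier than it need be. If it is collected but not named in advance, adjusting for it becomes a choice made after the data are seen.

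The second issue is whether data and model fit together. A yes/no record of any visit cannot show a repeat visit, which Aim 2 names, and cannot supply the count that the Poisson model requires.

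**Working it through.** **No figure to reproduce.** The documents give no rate, variance, effect size or power for utilisation. The steps below illustrate size. The SAP supplies six clinics, 224 children per clinic and the six clinic rates in step 1; every other input is assumed and marked so.

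**1. How far six clinics can differ by chance.** Inputs: the six clinic rates that the SAP uses to derive its intra-class correlation (15, 20, 25, 30, 35, 40%). These concern the primary outcome, so they are only a guide. Their mean is 27.5%, and their SD divided by the mean is 0.31. A 3:3 split is assumed, because the documents do not state the number of clinics per arm. Over all 20 such splits, with no treatment effect:
- SD of the arm difference: 7.6 points
- maximum difference: 15 points
- splits differing by at least 5 points: 14 of 20, or 70%

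**2. The same on a rate-ratio scale.** Let CV be the between-clinic coefficient of variation in use, and r the clinic-level correlation between prior and later use (both assumed). Leaving out sampling variation within clinics,

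SD(log rate ratio) = CV × √(1/3 + 1/3) × √(1 − r²).

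For CV = 0.20 and no baseline (r = 0): 0.20 × 0.816 = 0.163, so the 95% chance range is exp(±1.96 × 0.163) = 0.73 to 1.38. With CV 0.10 it is 0.85 to 1.17; with CV 0.30 it is 0.62 to 1.62.

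Adjusting at CV = 0.20:

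| r | SD | 95% chance range |
|---|---|---|
| 0.5 | 0.141 | 0.76 to 1.32 |
| 0.8 | 0.098 | 0.83 to 1.21 |
| 0.9 | 0.071 | 0.87 to 1.15 |

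**3. Child-level simulation under no effect.** Step 2 treats the clinic's prior level as known. In practice the covariate would be each child's own prior count, which is noisy. Assumed: 3 v 3 clinics, log-normal child propensity with SD 0.8, clinic SD 0 to 0.2 on the log scale, and clinic level correlated 0.7 to 0.9 between years. The unadjusted difference in mean log clinic rate was compared with the difference from a Poisson model with clinic terms and log(1 + prior-year count).

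| Mean events a year | Stability of child propensity between years | Fall in SD of log rate ratio |
|---|---|---|
| 2 | 1.0 (perfect) | about 24-40% |
| 2 | 0.6 | about 2-25% |
| 0.3 | 0.6 to 1.0 | about 0-12% |

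As an example from the first row, at clinic SD 0.2 and clinic correlation 0.7 the SD falls from 0.174 to 0.120, that is 1 − 0.120/0.174 = 31%. The ranges carry simulation error of a few percentage points.

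**4. Yes/no item against count.** For a Poisson count with mean L, the share of information on the rate ratio that survives recording only any against none is L/(e^L − 1). With assumed means:
- L = 0.5: 0.5/0.649 = 77%
- L = 1: 1/1.718 = 58%
- L = 2: 2/6.389 = 31%
- L = 3: 3/19.09 = 16%

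The loss is modest for rare events and large for common ones such as sick visits.

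**The case against.** **A baseline is not ruled out.** A reader might infer that pre-screen utilisation does not exist or cannot be had. The documents do not support that. The inclusion rule in q23234 says which children enter the review, not how far back their records go. The utilisation list has no date window, and q30004b and q30004d foresee linking past data to study outcomes. What stands is that no past utilisation is specified, either as a data pull or as a covariate.

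**Adjustment is planned.** A reader might also infer that differences between clinics will be read as an effect of the module, that is, as bias. Clinics are randomised, the SAP adjusts for patient and clinic characteristics, and the cluster factor brings between-clinic variation into the standard error. This disposes of systematic bias. It does not remove an imbalance that has occurred, and the unspecified covariates cannot be assumed to include prior use.

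**The gain may be small.** It would be tempting to quote the top row of the simulation table as the benefit. That row needs each child's propensity to be perfectly stable, which is doubtful when SAP Table 3 expects 20-70% of children to improve within 3 months. For rare events such as emergency visits or admissions, the gain may be close to nothing. This objection stands, and it limits the claim.

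**Counts can probably be derived.** That repeat visits cannot be counted at all would also go too far. The protocol (q22123) plans Epic and INPC queries of visits and stays, which could yield counts, and q724 says that no data collection form is used. The lists may be loose wording on an ethics form. Even so, they are the protocol's statement of what is recorded, they appear in three places, and they differ from the SAP.

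**Conclusion.** The point holds as a recommended, inexpensive improvement to a secondary analysis. It does not touch the primary outcome.

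- **Prior use is unspecified.** The consequence is lost precision and chance imbalance between six clinics. Under a between-clinic CV of 0.20, chance clinic differences alone could put the arm rate ratio anywhere from 0.73 to 1.38. How much of that adjustment recovers is uncertain: from almost nothing for rare events to about 40% of the SD in the most favourable case. These figures rest on assumed event rates, clinic variation and year-to-year stability.
- **Data points and model disagree.** This is a conflict of wording between protocol and SAP. It needs no assumption to establish and should be reconciled whatever is decided about the covariate.

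**What to change.** 1. **Query.** Extend the Epic and INPC utilisation query to the 12 months before each child's index screen. End the window at the screen, so that the module cannot influence the covariate.
2. **Model.** In the SAP, name prior-period use of the same outcome as a covariate in each Poisson model. Do this before any outcome data are examined.
3. **Children with under 12 months of look-back.** Use a prior rate with an indicator for short or no look-back, or an interaction with age group, or the clinic's prior-year rate. An offset on the outcome is not a remedy: it adjusts the exposure time of the outcome, not a covariate measured over a shorter period.
4. **Data points.** In q725, q23650 and item 9010 of the Administrative Details Form, define visits, tests, procedures and prescriptions as dated events, so that counts and repeat visits can be computed.

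The cost is a slightly larger records query, one covariate per model and a wording amendment. No patient contact or extra recruitment is needed. Little gain should be expected for infants.
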